Supervision and limit setting: Parents are given information and practice opportunities for managing behavior in toddler years, ignoring unwanted behavior, setting limits, and keeping the home a safe environment.

Consumer Satisfaction/Exit Interview The 2-page website feedback survey administered at the end of the pilot study asks questions about acceptability, usability of the FCU Online as well as questions about working with a Family Consultant, and suggestions for improvement to the study procedures/content (see attachment "Rural Opioid website satisfaction survey and exit interview"). The consumer satisfaction/exit interview will take approximately 20 minutes.

3. Clinical trial research study (n=400 parents).

After incorporating feedback from the pilot study to materials and process, we will begin the clinical trial phase of the study, where we will recruit 400 English or Spanish speaking families with a child between the ages of 18 months and 5 years old. Two hundred families will be randomly assigned to an intervention condition where participants complete four phone interviews/ surveys over the course of a year and receive the FCU along with coaching from a Family Consultant; two hundred families will be randomly assigned to a control condition where participants complete four phone interviews/surveys over the course of a year and are given access to the FCU at the conclusion of their study participation (e.g., one year later). A quick completion bonus of \$25 will be offered to families at each wave of data collection, if they complete a phone interview or survey within 2 weeks of it being offered to them. Families in the control condition will not receive coaching from a Family Consultant. All families will also be invited to opt into using the EARS tool, which is installed on the participant's phone and collects passive data to record naturalistic behavior related to mental health. Parents will have the opportunity to receive up to \$425 in one year for participating in the study or up to \$400 if they opt out of the EARS component. All research activities will be available to be conducted in either English or Spanish, depending on the preference of each family.

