RESEARCH HYPOTHESES. We will assess the feasibility of the FCU as an Internet-delivered intervention in rural communities with high levels of opioid use, including the extent to which participants engaged in the intervention, completed the program, and were satisfied with the program. We hypothesize that the FCU Online intervention will demonstrate feasibility based on benchmark analyses described below. We also hypothesize that website usage (dosage) and coach fidelity will be associated with significantly greater change in the primary and secondary outcomes.

SAMPLE SIZE AND POWER. With a sample size of 127 in the intervention condition (accounting for 15% attrition), with alpha set to .05 (two-tailed), there is sufficient power ($>.80$) to detect $r = .25$ (moderate effects) for the process analyses involving treatment acceptability, fidelity, and engagement.

Data Management and Analysis for Supplement Pilot Aim

Data management systems similar to those used in our other web-based research projects will be used to ensure the integrity of the analytic results. These systems entail the creation of scheduling algorithms and web-based data collection forms for each instrument, including backup and protection routines that ensure confidentiality and preservation of the electronic records. We will use accepted practices for handling missing data when appropriate. Maximum likelihood methods with time as a random variable, such as the mixed effects regression models described below, allow the use of all available data and reduce bias associated with attrition and increasing power. These procedures can provide unbiased conclusions even with substantial attrition. We anticipate a participation rate through three months of at least 85% based on our previous FCU school-based efficacy trials and our current rate of participation and retention in our FCU Online RCT (90%).

Aim 1: Adapt the FCU Online for young adult parents with a history of substance misuse using a prevention framework

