Usability. We will assess participants' quantitative ratings during the usability testing phase in which the benchmark for acceptable ratings will be mean ratings of 4 or greater on a 5-point scale for each of the System Usability Scale (SUS) items and an overall SUS rating of 80.3, which represents an "A" score. Program acceptability will also be demonstrated by (a) high level of program usage (e.g., 80% of participants complete the FCU assessment and feedback sessions), and (b) high degree of consumer satisfaction (e.g., mean ratings > 4 on a 5-point rating scale across satisfaction domains).

Aim 2: Conduct a pilot test of the efficacy of the adapted FCU Online developed in Aim 1.

Statistical design. Individual participants will be randomized to condition and will therefore be the unit of analysis in tests of condition effects in all statistical models. The pilot study will use a pre-post between-group design to examine differences between conditions in the intervention targets assessed at baseline and postintervention (3-month assessment point). Due to the limited sample size and duration of the pilot study, we do not expect to find differences between conditions for the more distal outcomes of opioid misuse or OUD.

Intervention effects and statistical power. We expect that participants receiving the FCU Online intervention will demonstrate improvements in the intervention targets compared to those assigned to the treatment-as-usual control condition. We will examine descriptive statistics and pre-post data to evaluate trends and outcomes, which will provide us with preliminary data to support further research with this population. Mixed-effects regression models will be used to examine post-test differences in the intervention targets between

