Statistic design and analyses. Analysis of outcomes assessed during the one-week bursts of passive or active data collection methods surrounding each assessment time point will involve alternative mixed-effects models appropriate for measurement-burst study designs. Briefly, subjects (Level 3) will undergo three assessment time points (Level 2). Each time point will involve passive and active data collection methods that generate repeated measures of key study variables at Level 1 (e.g., moment-level affective tone, sleep routines, mood state, coping skills, and stress). The corresponding three variances of these mixed-effects models are between-subjects (BS), within-subjects-between-time points (WS-BTP) and within-subjects-within timepoints (WS-WTP). Unconditional models will describe the degree of BS, WS-BTP, and WS-WTP variability in outcomes. Conditional models will be specified to investigate whether study condition predicts variability in outcomes at each of these levels. Models will include random intercept and time effects to account for individual heterogeneity in levels within and trends across time points, as well as random effects for condition to allow heterogeneity across subjects in effects on outcomes. Because the pilot study is underpowered, we will use standard deviation effect sizes ($d > .30$) as the benchmark for determining clinically meaningful effects.

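### Supplement Aim 3: with individual randomization a random condition effect cannot measure heterogeneity in individual effects, and the SAP's count of assessment time points needs reconciling

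*SAP*

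**What the plan says.** All of the following is in the SAP's part on the supplement pilot, unless the protocol is named.

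- **Aim 3, Statistic design and analyses, design.** One-week bursts of sensing data are placed around each assessment, and "subjects (Level 3) will undergo three assessment time points (Level 2"). Three variances are named: between subjects (BS), within subjects between time points (WS-BTP), and within subjects within time points (WS-WTP).
- **Aim 3, random intercept and time.** "Models will include random intercept and time effects to account for individual heterogeneity in levels within and trends across time points".
- **Aim 3, random condition effect.** The same sentence goes on to add a further term: "as well as random effects for condition to allow heterogeneity across subjects in effects on outcomes". Neither the covariance structure nor the coding of condition or time is given.
- **Aim 3, condition and variability.** "Conditional models will be specified to investigate whether study condition predicts variability in outcomes at each of these levels".
- **Aim 2, Statistical design.** "Individual participants will be randomized to condition and will therefore be the unit of analysis". The design is pre-post, with "intervention targets assessed at baseline and postintervention (3-month assessment point").
- **Data Management and Analysis for Supplement Pilot Aim.** "We anticipate a participation rate through three months of at least 85" per cent.
- **Protocol, Methods and Materials, Clinical trial research study.** There are four research assessments: baseline, 3 months, 6 months and 1 year. The EARS phone tool is installed at or shortly after the baseline assessment and deleted at the 3-month assessment. Control families "are given access to the FCU at the conclusion of their study participation (e.g., one year later").

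**The concern.** A random effect shows how an effect varies across subjects only if the predictor varies within subjects. Here each subject is in one arm, and controls get the program about a year later, after EARS has been deleted. The data therefore hold no within-subject contrast of conditions. Software may still print a variance for the term, and the SAP's stated purpose for it invites a reader to take that number as variation in individual treatment response. The pilot is meant to inform further research, so such a figure could be carried forward.

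The count matters because it decides whether the random time effect can be estimated next to a WS-BTP variance. Three time points allow it; two, under plausible specifications, do not.

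**Working it through.** **The plan's own figure.** The pilot's power is given as below .50 for d = .30, 100 participants, two-sided alpha .05. With 50 per arm (1:1 assumed): .30 × √(50/2) = 1.50, and Φ(1.50 − 1.96) = 0.32. This agrees, and nothing below depends on it.

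**Step 1. Count the time points.**

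| Source | Time points |
|---|---|
| SAP, supplement Aim 3 | 3, not listed |
| SAP, supplement Aim 2 | 2 (baseline, 3 months) |
| Protocol research assessments | 4 (baseline, 3, 6, 12 months) |
| Protocol assessments adjoining the EARS window | 2 (baseline, 3 months), with continuous recording between |

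No section lists three.

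**Step 2. The random condition effect.** Let a be the random-intercept variance, g the random-condition variance, c their covariance, w the WS-BTP variance and e the WS-WTP variance. For condition code x, the between-subject variance in an arm is

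V(x) = a + 2xc + x²g.

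- 0/1 coding: V(0) = a and V(1) = a + 2c + g.
- -0.5/+0.5 coding: V = a − c + .25g and V = a + c + .25g.

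However many bursts there are, the data supply two arm variances plus w and e, which is four quantities.

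| Covariance c | Coding | Parameters | Rank | What g is |
|---|---|---|---|---|
| free | either | 5 | 4 | not identified |
| zero | 0/1 | 4 | 4 | V(1) − V(0), an arm difference in BS variance |
| zero | -0.5/+0.5 | 4 | 3 | confounded with a |

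Numerical ranks of the implied covariance matrix (7 daily values per burst assumed) gave these results at 2, 3, 4 and 13 time points. With random time and its covariance with the intercept also in the model, and c free, there are 7 parameters with rank 6 at three bursts, so a third burst is no cure. If the SAP's plan to let condition predict variability means arm-specific variances, g is also redundant: 7 parameters, rank 6, even with c set to zero.

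The SD of an individual effect is √(v1 + v0 − 2ρ√(v1·v0)). Here v0 and v1 are the between-subject variances in the two arms and ρ is the correlation between a subject's outcomes under the two conditions. No subject is seen under both, so ρ is never observed. With v0 = v1 = 1 (assumed):

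| ρ | 1 | .8 | .5 | 0 | −1 |
|---|---|---|---|---|---|
| SD of effect | 0 | 0.63 | 1.00 | 1.41 | 2 |

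All five fit the same data.

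**Step 3. Random time, only if two bursts are kept.** Code time 0, 1 by burst. Let s be the random-time variance and k its covariance with the intercept:

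Var1 = a + w; Cov = a + k; Var2 = a + 2k + s + w.

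That is three burst-level moments for four parameters. With e added, it is 5 parameters with rank 4. For example, (a, s, k, w) = (1, .2, 0, .3), (1.1, .4, −.1, .2) and (1.3, .8, −.3, 0) all give Var1 = 1.3, Cov = 1.0, Var2 = 1.5. With three bursts the rank is 5 of 5. Without random time, two bursts give 3 of 3.

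Setting k = 0 is not a way out, because coding then decides the answer. From the same moments, coding the first burst 0 gives w = .30 and s = .20. Coding the last burst 0 gives w = .50 and s = −.20, which is inadmissible.

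**Step 4. Precision of an arm variance ratio.** With 50 per arm and no measurement noise (both assumed), F(.975; 49, 49) = 1.762. The 95% limits around a BS ratio of 1 are 1/1.762 = 0.57 to 1.76.

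**The case against.** The strongest reply is that Aim 3 describes its models only briefly, calls them alternatives and leaves covariance and coding open. With zero covariance and 0/1 coding the random condition variance can be estimated, and the only criterion stated is d > .30. This is fair as far as it goes: the SAP does not say it will report that variance as individual response. But it does give heterogeneity in effects as the term's purpose, and no coding or covariance choice serves that purpose. One could also read condition as exposure that starts after baseline. The SAP does not say so, and with two bursts and free covariances such a term would be aliased with random time in the treated arm.

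On the count, Aim 2 says when intervention targets are compared; it does not exclude a further assessment. That stands, and it is why the request is to reconcile the sections, not to declare three wrong.

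Two stronger readings are tempting and are not supported. A reader might infer that EARS yields only two bursts. EARS records continuously between baseline and 3 months, Aim 3 does not name the tool, and the SAP (2019) predates the protocol (2025). What is two is the number of protocol assessments adjoining the EARS window. A middle week could be cut from the record, but no section defines one. A reader might also infer that the random time model fails as planned. With the three time points that Aim 3 states, it is identified.

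**Conclusion.** The concern holds in two parts. First, the random condition effect cannot measure heterogeneity in individual effects at any number of bursts. This follows from individual randomization and does not depend on sample size. Second, the SAP gives three time points in Aim 3 and two in Aim 2 of the same pilot. The random-time problem is conditional: it needs two bursts, burst-coded time, free covariance and a separate WS-BTP variance in one model. The three-variance split on its own remains identified with two bursts.

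The point is minor. It concerns one clause and one count in the third aim of a pilot that avoids formal hypothesis testing. Nothing here changes the d > .30 benchmark, a sample size or a power figure. The ranks assume 7 daily values per burst; the ratio limits assume 50 per arm and no measurement noise.

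**What to change.** 1. Replace the random condition effect with fixed condition and condition-by-time terms.
2. If arm differences in variability are of interest, let the BS, WS-BTP and WS-WTP variances differ by arm. Report variance ratios with intervals, and state that they are not individual treatment response. They will be imprecise at this sample size.
3. Reconcile the number of time points across supplement Aims 2 and 3 and the EARS schedule, and state when each burst falls.
4. If two bursts are kept with burst-coded time, omit random time. Do not rely on a zero-covariance constraint instead.

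The cost is SAP rewording, with no new data collection. Omitting random time gives up individual trends across bursts. Dropping the random condition effect gives up nothing that the data could have shown, since item 2 covers any arm difference in variance.
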